### 9.2.2 *Reporting Serious Adverse Events (SAE)*

All SAEs **must be reported immediately** by the Investigator to Guerbet. Therefore, the Investigator must immediately forward to Guerbet Pharmacovigilance department a duly completed report form for SAE or AESI (F001406) provided by Guerbet with trial documents, even if it is obvious that more data will be needed in order to draw any conclusion:

- By e-mail to: [[contact]](mailto:[contact])

 CONFIDENTIAL	Protocol No. GDX-44-015 Version No. 4.0 including amendments 1 & 2 & 3 Date 09 Oct 2023	F015919-05 Page 53 / 75
--	---	----------------------------

In case of emergency, Guerbet Pharmacovigilance department may be contacted at:

**[name].**

SAEs occurring at any time during the patient's participation to the trial have to be reported also in medical file and in the appropriate section of the eCRF (see [9.1.2](#))

In order to allow the assessment and eventual subsequent regulatory reporting of the case, the following minimum information should be filled in:

- Patient's details including date of birth/age, sex and patient's trial identification number
- Patient's medical history relevant to the assessment of the event
- Type of event by reporting a diagnosis or if not available, symptoms
- Date and time to onset of the event
- End date of the event (will be reported in a follow-up report if the event is still ongoing at the time of initial notification)
- Date and time of investigational drug administration,
- Seriousness criterion
- Causal relationship to the investigational drug or procedure (mandatory)
- Outcome at the time of reporting

If the Investigator is aware of any new relevant information concerning a SAE (e.g.: outcome or any information that can have an impact on the assessment of the seriousness or the causal relationship between the SAE and the IMP), he has to send immediately to Guerbet Pharmacovigilance department the report form for SAE or AESI duly completed (F001406).

In order to comply with current regulations as well as for comprehensive assessment purposes, additional information (e.g. autopsy results, biological values...) or clarifications may be required by Guerbet in a timely fashion to ensure accurate follow-up and assessment of each case and should be transmitted, anonymized, with a specific form (F018362) as soon as they are available.

SAEs should be followed up by the Investigators until complete recovery of the patient or, if not possible, until stabilization of sequelae.

SAEs associated with trial procedures are to be notified using the same reporting procedure as described above.

According to local requirements, Guerbet or its representatives will communicate relevant safety information to the appropriate Agency(ies), IEC and/or all active Investigators, as it becomes available.

The transmission of the information to Guerbet does not release the Investigator from his responsibility to inform the regulatory authorities and or IEC/IRB, if applicable.

### 9.3 Special situations

#### 9.3.1 *Cases of overdose, lack of efficacy, interaction with drug or device, medication errors or misuses*

The safety information regarding the following special situations has to be collected and reported by the Investigator with the same procedure as for AE, even if uneventful:

- Medication error: an unintended failure in the drug treatment process that leads to, or has the potential to lead to, harm to the patient (e.g.: wrong route of administration). A failure in the drug treatment process does not refer to lack of efficacy of the drug, rather to human or process mediated failures

 CONFIDENTIAL	Protocol No. GDX-44-015 Version No. 4.0 including amendments 1 & 2 & 3 Date 09 Oct 2023	F015919-05 Page 54 / 75
--	---	----------------------------

- Misuse: where the medicinal product is intentionally used not in accordance with the protocol,
- Occupational exposure to an IMP: an exposure to a medicinal product as a result of one's professional or non-professional occupation
- Suspected drug-drug or drug-device interaction with another product.
- Unusual Lack of efficacy: for Guerbet imaging products, lack of efficacy is mainly represented by cases of "lack of contrast" or "poor iconographic quality" or "no contrast" or "poor contrast" etc.
- Overdose: administration of dose above the 0.3 mmol/kg for gadopiclenol.

### 9.3.2 *Pregnancy*

Not applicable.

### 9.3.3 *Adverse Events of Special Interest*

An Adverse Event of Special Interest (AESI), serious or non-serious, is one of scientific and medical concern specific to the sponsor's product or programme, for which ongoing monitoring and rapid communication by the Investigator to the sponsor can be appropriate. Such an event might warrant further investigation in order to characterize and understand it.

For Guerbet, the transmission of an AESI to the Guerbet Pharmacovigilance Department respects the same time frame as an SAE and should be reported using the report form for SAE, AESI (F001406).

The AESI for this protocol is the following: Nephrogenic Systemic Fibrosis (NSF).

### 9.3.4 *Any suspicion of transmission of an infectious agent via an IMP*

Any suspicion of transmission of an infectious agent via an IMP should be considered as serious and processed as an SAE.

## 9.4 Other important safety issue / new fact

Any new data which may lead to a reassessment of the benefits / risks balance of the research or product being studied, changes in the use of that product, the conduct of the research or documents relating to the trial, or to suspend or interrupt or modify the protocol of the trial, or similar searches have to be evaluated by Guerbet.

It may include any new event likely to affect the safety of the patient's and that may be related to the conduct of the trial or the development of the trial drug such as:

- A SAE which could lead to the modification of the conduct of the trial (ex: SAE associated with the trial procedures, SUSAR).
- A significant hazard to the patient population such as lack of efficacy of an IMP used for the treatment of a life-threatening disease (if applicable).
- A new major finding from an animal study,
- A temporary halt of a trial for safety reasons if the trial is conducted with the same IMP in another country by the same sponsor,
- Recommendations of the Safety Committee/TSRB, if any, where relevant for the safety of patient,
- Increase in the frequency of an expected event considered as clinically significant.

Guerbet    CONFIDENTIAL	Protocol No. GDX-44-015 Version No. 4.0 including amendments 1 & 2 & 3 Date 09 Oct 2023	F015919-05 Page 55 / 75
--	---	----------------------------

According to local requirements, Guerbet or its representatives will communicate relevant safety information to the appropriate Agency(ies), IEC/IRB and/or all active Investigators, as it becomes available.

Consequently, this type of important safety issue might lead also to:

- Urgent safety measures and their notification
- Substantial trial documents modifications
- Premature discontinuation of the trial
- Premature discontinuation of the patient

## **9.5 Unblinding Procedures**

Not applicable.

 CONFIDENTIAL	Protocol No. GDX-44-015 Version No. 4.0 including amendments 1 & 2 & 3 Date 09 Oct 2023	F015919-05 Page 56 / 75
--	---	----------------------------

## 10 SCREEN FAILURE AND PREMATURE DISCONTINUATION

### 10.1 Screen failure

A patient whose parent(s) or legal guardian (where applicable) have signed the informed consent and who discontinue the trial before IMP injection will be considered screening failure. The reason for screening failure will be documented. Such patient can be re-screened according to the same modalities as for the new patient. Particular attention must be paid in order not to exceed overall trial-related blood loss limit of 0.9 mL/kg body weight corresponding to 1% of total blood volume at a single time point and 2.4 mL/kg body weight (3% of the total blood volume) during a period of four weeks.

A new patient number will be allocated to the patient.

Data to be collected for screen failure patients: refer to [14.3.2](#)

### 10.2 Premature Discontinuation of the trial per Guerbet Decision

Guerbet reserves the right to discontinue the trial at any time for medical, administrative or other reasons. Guerbet will inform the relevant authorities in each country, the ethics committees, the trial site Investigators, pharmacists and hospital authorities according to the regulatory texts in force.

### 10.3 Premature discontinuation of the patient

Premature discontinued patients are defined as patients whose parent(s) or legal guardian (where applicable) have signed the informed consent and are discontinued from the trial after being administered with IMP.

Data collected for premature discontinued patients: Please refer to [14.3.2](#).

### 10.4 Reasons for patient's screening failure and premature discontinuation

Criteria for screen failure and premature discontinuation of patients:

- Inclusion criteria not met /Non-inclusion criteria met;
- Adverse Event (according to the Investigator's judgement)
- Adverse Event of Special Interest (AESI);
- Withdrawal of patient's parent(s) or legal guardian (where applicable) consent:

If the patient's parent(s) or legal guardian withdraws consent for disclosure of future information, Guerbet may retain and continue to use any data collected before such a withdrawal of consent.

If a patient withdraws from the trial, his/her parent(s) or legal guardian may request destruction of any samples taken and not tested, and the Investigator must document this in the site's records.

- Patient lost to follow-up (date of last contact will be documented in the medical file and the eCRF). Any effort will be undertaken to know the reason for this loss to follow-up and/or to exclude any adverse reaction as this reason. This will be documented in the patient's medical file;
- Discovery of an unexpected, significant, or unacceptable risk to the patients enrolled in the trial:

Guerbet    CONFIDENTIAL	Protocol No. GDX-44-015 Version No. 4.0 including amendments 1 & 2 & 3 Date 09 Oct 2023	F015919-05 Page 57 / 75
--	---	----------------------------

- At the discretion of the Investigator if the patient safety or well-being is not compatible with trial continuation:
- Deviation from plan as specified in the protocol or deviation affecting primary criteria (e.g. trial specific assessment not performed):
- Other reason in case patient's screen failure or premature discontinuation is not related to any of the listed reasons

#### **10.5 Enrollment of additional patient:**

All patients prematurely discontinuing the trial for whom 3 blood sampling for PK analyses within 3 time windows were not performed, will be replaced.

The enrollment will continue in order to ensure an overall number of 50 included patients (including 25 patients in CNS cohort) and minimum numbers of evaluable patients per age group (Group 1: at least 20 patients; Group 2: at least 12 patients and Group 3: at least 5 patients).

In the event of premature discontinuation, patients will receive adequate follow-up and usual medical care from site Investigators.

## 11 STATISTICAL CONSIDERATIONS

The following sections summarize the statistical considerations, which are fully described in the Statistical Analysis Plan.

### 11.1 Statistical Method

The trial aims to evaluate the pharmacokinetic plasma profile of gadopiclenol in a pediatric population aged from birth to 23 months. In order to minimize the clinical burden to children, only 3 samples per patients will be allowed, so, a population PK analysis, which is a suitable approach to characterize the PK with sparse blood sampling, will be performed to determine primary pharmacokinetic parameters. These parameters will be then summarized through descriptive statistics.

Therefore, no inference will be done from this trial and therefore no null or alternative hypotheses are needed.

### 11.2 Sample Size

The sample size was determined in order to optimize the characterization of gadopiclenol pharmacokinetics in pediatric population through population PK modelling. Sample size determination was coupled with evaluation of the PK sampling scheme recommended by FDA for the evaluation of the PK of Dotarem® in the same population of infants aged between 0 and 2 years [21].

Simulations were performed in order to evaluate the performance of the design and the sample size, using gadopiclenol popPK model for adult and children aged between 2 and 17 years refined to account for renal maturation in infants.

The design evaluation was performed for a sample size of 45 subjects evaluable for the primary criteria, as achieved in Dotarem® trial, and for 40 subjects.

Results were expressed as median of estimated parameters and precision (%RSE) calculated on successful estimation process performed on 200 simulated cases and presented in **Table 3: Evaluation of the design for 45 subjects.** and **Table 4: Evaluation of the design for 40 subjects.** below.

**Table 3: Evaluation of the design for 45 subjects.**

Parameters	Typical values	Successful runs (/200)	Parameters Estimate	Bias	Precision (RSE%)
	Children	N	Median	Mean	Median
CL (L/H)	5.8	177	5.83	0.03	4.00
V1 (L)	7.76	177	7.47	-0.39	16.00
Q (L/H)	4.48	177	4.84	0.46	22.00
V2 (L)	4.41	177	4.63	0.18	14.00
IIV CL	0.0379	177	0.04	-0.00	27.00
IIV V1	0.0354	177	0.04	0.02	95.00

Parameters	Typical values	Successful runs (/200)	Parameters Estimate	Bias	Precision (RSE%)
	Children	N	Median	Mean	Median
IIV Q	NA	177			-
IIV V2	NA	177			-
$\sigma$	0.0372	177	0.04	-0.00	16.00

**Table 4: Evaluation of the design for 40 subjects.**

Parameters	Typical values	Successful runs (/200)	Parameters Estimate	Bias	Precision (RSE%)
	Children	N	Median	Mean	Median
CL (L/H)	5.8	168	5.85	0.03	4.00
V1 (L)	7.76	168	7.55	-0.27	16.00
Q (L/H)	4.48	168	4.73	0.44	23.00
V2 (L)	4.41	168	4.57	0.13	15.00
IIV CL	0.0379	168	0.03	-0.00	27.00
IIV V1	0.0354	168	0.04	0.03	97.00
IIV Q	NA	168	0.00	-	-
IIV V2	NA	168	0.00	-	-
$\sigma$	0.0372	168	0.04	-0.00	17.00

Overall, the sampling design with either 45 or 40 subjects will allow to estimate all fixed parameters with an excellent precision (RSE<=20%). The between subject variability for CL and residual error will be also very well captured (RSE<30%). Only the variability for the central volume of distribution could be poorly estimated if the infant's data cannot be combined with other data (stand-alone infant model). With only 3 samples to be taken by infant, it is anticipated that between-subject variability on volumes of distribution could not appropriately estimated, even with larger sample size, and this is not considered as a relevant issue invalidating the sampling design, because this variability is of limited interest as far as the IIV for CL is correctly estimated. Increasing the sample size will improve moderately the estimation of the between subject variability on volume of distribution, in case of infants' data cannot be pooled with other data collected in adult, children and adolescents.

Assuming that about 10% of patients included in the trial will not be evaluable for the primary criteria, a sample size of 50 patients, in agreement with the pediatric plans (PIP/PSP), will allow to achieve the trial's objectives.

 CONFIDENTIAL	Protocol No. GDX-44-015 Version No. 4.0 including amendments 1 & 2 & 3 Date 09 Oct 2023	F015919-05 Page 60 / 75
--	---	----------------------------

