## 8 STUDY DATA

### 8.1 JUSTIFICATION FOR THE NUMBER OF SUBJECTS

The sample size was determined in order to optimize the characterization of gadopiclenol pharmacokinetics, with a good precision of parameters, in pediatric population through popPK modelling, which is the study primary objective. Sample size determination was coupled with evaluation of the PK sampling scheme recommended by FDA for the evaluation of the PK of Dotarem® in the same population of pediatric patients aged between 0 and 2 years.

Simulations were performed in order to evaluate the performance of the design and the sample size, using gadopiclenol popPK model for adult and children aged between 2 and 17 years, refined to account for renal maturation in pediatric population <2 years.

The design evaluation was performed for a sample size of 45 subjects evaluable for the primary criteria, and for 40 subjects. Overall, the sampling design with either 45 or 40 subjects will allow to estimate all fixed parameters (clearances and volumes) with an excellent precision (Relative standard error (RSE) <=20%). The between subject variability for clearance (CL) and residual error will be also very well captured (RSE<30%). Only the variability for the central volume of distribution could be poorly estimated if the pediatric population <2 years data cannot be combined with other data (stand-alone pediatric population <2 years model).

With only 3 samples to be taken by pediatric population <2 years, it is anticipated that inter-individual variability (IIV) on volumes of distribution could not appropriately estimated, even with larger sample size. This is not considered as a relevant issue invalidating the sampling design, because this variability is of limited interest as far as the IIV for CL is correctly estimated. Increasing the sample size will moderately improve the estimation of the IIV on volume of distribution, in case of pediatric population <2 years data cannot be pooled with other data collected in adult, children and adolescents.

Assuming that about 10% of patients included in the trial will not be evaluable for the primary criteria, a sample size of 50 patients, in agreement with the pediatric plans (PIP/PSP), will allow to achieve the study objectives.

	PH21036 / GDX-44-015 Analysis Plan Version 2.0: 29/10/2024	gadopiclenol Page 11/30
---	---	----------------------------

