### 9.1 SEQUENCE OF PLANNED ANALYSIS

The popPK model will be developed according to the following strategy:

1. Preliminary checks will be performed to assess whether the existing model is predictive of data collected in pediatric patients <2 years. If it is the case, data from these pediatric patients will be

	PH21036 / GDX-44-015 Analysis Plan Version 2.0: 29/10/2024	gadopiclenol Page 15/30
---	---	----------------------------

added to previous data in order to update the existing model, otherwise, only pediatric population <2 years data will be used for model development

2. On the selected dataset (only pediatric population <2 years or pediatric population <2 years added to previous data), selection of the simplest structural model, which predicts the plasma concentrations as a function of time and dose, based on smallest objective function and by the pattern in the residual plots. The best estimation method, the most appropriate IIV models, and the residual error model, will be identified. The resulting model is called BASE. In this model, population specificities will be accounted for as structural covariates.
3. Graphical exploration of the covariates: between individual covariates and post-hoc (FO) or conditional (FOCE) parameter estimates and between covariates and conditional weighted residuals (CWRES).
4. Determination of the covariate model using a backward deletion process:
  - a. Univariate analysis (covariates are added only to parameters having  $\eta$  in BASE).
  - b. Multivariate analysis: all selected covariates are added together, the model is fit to data and a new value of objective function (OFV) will be obtained and considered as a reference called FULL model
  - c. Selection of significant covariate to obtain the FINAL model

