## 9.3 STRUCTURAL PHARMACOKINETIC MODEL

The population PK model selected on previous data was a two-compartment model with elimination from the central compartment. The model was parameterized in terms of clearance (CL), central volume of distribution ( $V_1$ ), inter-compartment clearance (Q) and peripheral volume of distribution ( $V_2$ ). All parameters were scaled to body weight using fixed allometric rules. The CL was also scaled to eGFR with a power model for pediatric population and a Gompertz function for adult population. Ethnic population covariate was

	PH21036 / GDX-44-015 Analysis Plan Version 2.0: 29/10/2024	gadopiclenol Page 16/30
---	---	----------------------------

applied on all parameters. Exponential models were used to describe the inter-individual variability on CL,  $V_1$  and  $V_2$  and a proportional model was considered as error.

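### The claim that every fixed PK parameter is estimated with RSE of at most 20% is contradicted by the protocol's own tables: Q is at 22% (45 infants) and 23% (40 infants)

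*Protocol*

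**What the plan says.** Protocol 11.2 evaluates the sampling design by simulating 200 trials at each of two sizes, 45 and 40 evaluable infants. It reports median estimates and precision "calculated on successful estimation process performed on 200 simulated cases". Table 3 gives the results for 45 infants and Table 4 those for 40. Below the tables the protocol concludes that "the sampling design with either 45 or 40 subjects will allow to estimate all fixed parameters with an excellent precision (RSE<=20"%). It adds that IIV on CL and the residual error have RSE below 30%, and names the variability of the central volume as the only quantity that could be poorly estimated.

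SAP 8.1 carries the claim over without the tables and spells out its scope: the design "will allow to estimate all fixed parameters (clearances and volumes) with an excellent precision (Relative standard error (RSE) <=20"%). SAP 9.3 sets out the four structural parameters as CL, V1, V2 and the "inter-compartment clearance (Q").

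On the data to be fitted, SAP 9.1 adds the infants to the earlier data if the existing model predicts them; "otherwise, only pediatric population <2 years data will be used for model development".

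**The concern.** The summary sentence and the tables above it disagree on one of the four fixed parameters, at both sample sizes. The protocol text names no exception for Q. By singling out only the central-volume variability as a weak point, it suggests that every fixed effect met the bound. A reader of the SAP alone cannot discover the exception, because the tables are not reproduced there.

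The sentence also drops two qualifiers that can be found elsewhere in protocol 11.2. The RSEs are medians over successfully estimated runs only, and the tables show NA for the typical values of IIV on Q and V2.

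The stake is limited but real. The sentence supports the adequacy of the design in both documents. Q is not a listed primary parameter, but it enters quantities that are: the terminal half-life (SAP 11, through the rate constants) and the simulated concentrations at 10, 20 and 30 minutes. The tables most directly describe a stand-alone infant fit, which remains a planned route if the preliminary checks fail.

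**Working it through.** **Inputs: median RSE (%) from protocol Tables 3 and 4**

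| Fixed parameter | N=45 | N=40 | At most 20%? |
|---|---|---|---|
| CL | 4 | 4 | yes |
| V1 | 16 | 16 | yes |
| Q | 22 | 23 | **no, at both sizes** |
| V2 | 14 | 15 | yes |

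**The plan's own figures**

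- Bound of 20% on all fixed parameters: max(4, 16, 22, 14) = 22 at N=45 and max(4, 16, 23, 15) = 23 at N=40. Not reproduced.
- Bound of 30% on IIV CL and residual error: 27% at both sizes, and 16% and 17%. Reproduced.
- Sample size: 45 / (1 - 0.10) = 50. Reproduced.

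**Could another reading rescue the 20% bound?**

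1. *Rounding.* If the entries are rounded to whole per cents, the lowest values consistent with them are 21.5 and 22.5. Both exceed 20.
2. *Scope.* Q is a typical-value row in both tables. The SAP's wording covers clearances, and SAP 9.3 defines Q as one.
3. *Denominator.* Taking the standard error relative to the true Q of 4.48 instead of the median estimate gives 22 x 4.84/4.48 = 23.8% and 23 x 4.73/4.48 = 24.3%. This moves further from the bound.
4. *All 50 infants evaluable.* This assumes that RSE scales with 1/sqrt(N). The tables are consistent with that: 22 x sqrt(45/40) = 23.3, against 23 tabulated.
   - From Table 3: 22 x sqrt(45/50) = 20.9% (20.4-21.4% allowing for rounding).
   - From Table 4: 23 x sqrt(40/50) = 20.6% (20.1-21.0%).
   - Still above 20%.

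Under the same scaling, the bound would be met at 45 x (22/20)^2 = 54.5 or 40 x (23/20)^2 = 52.9, that is about 53-55 evaluable infants (51-57 allowing for rounding). This only measures the size of the gap; it is not a proposal to enlarge the trial.

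**Related figures in the same tables**

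- Mean bias for Q: 0.46/4.48 = +10.3% (N=45) and 0.44/4.48 = +9.8% (N=40). This is the largest relative bias among the four. The next largest is V1, at -0.39/7.76 = -5.0% and -0.27/7.76 = -3.5%.
- Successful runs: 177/200 = 88.5% and 168/200 = 84.0%. The tabulated RSEs say nothing about the runs that failed.

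**The case against.** The best defence is that this changes nothing in the trial. N=50 follows from 45 evaluable infants and a loss of about 10%, not from the 20% bound, and no decision rule in the SAP uses that threshold. The synopsis calls the design appropriate without giving any RSE limit and, like protocol 11.2 and SAP 8.1, ties adequacy mainly to estimating IIV on CL correctly. That is met in the tables. Q misses by 2-3 points, and the correct figures stand directly above the sentence in the protocol. If infants are pooled with the earlier data, precision will differ anyway.

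All of this stands, and it limits the weight of the point. It does not make the sentence true, and the SAP reader does not have the tables.

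It can also be said that the documents never state outright that the tables come from an infant-only model or that IIV on Q and V2 was left out. Both are inferences. The first rests on the remark in protocol 11.2 about a stand-alone infant model, the second on the NA entries. They are reasonable inferences, but the sponsor should confirm them before they are written into the text.

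**Conclusion.** The concern holds. As worded, the statement is wrong for one of four fixed parameters at both sample sizes: at most 20% is claimed, and 22% and 23% are tabulated. This is read straight from the protocol and needs no modelling assumption; only the extrapolation to 50 infants relies on 1/sqrt(N) scaling.

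The documents do not show that the primary criteria are at risk. CL, and hence AUC, is at 4%. They give no RSE for half-life or for the 10-, 20- and 30-minute concentrations. A rough first-order Fisher information calculation with Table 3 values, 45 infants and assumed weights, ages and maturation gave 3-4% for half-life, 9-10% at 10 minutes, 4-5% at 20 minutes and 4% at 30 minutes for a 9.5 kg infant. It also returned 25-33% for Q instead of 22%, so it is indicative only and the conclusion does not rest on it.

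This should be corrected as a misstated design property. It is not a challenge to the sample size.

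**What to change.** Replace the sentence in protocol 11.2 and in SAP 8.1 with wording such as:

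> RSE is at most 16% for CL, V1 and V2; for Q it is 22% (N=45) and 23% (N=40). Values are medians over the 177/200 and 168/200 simulated trials with successful estimation, from an infant-only model without IIV on Q and V2.

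The sponsor should confirm the last clause. The essential part is the exception for Q.

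The cost is one sentence in each of two documents. No new simulation is required, and the sample size, sampling scheme and analysis stay as they are.

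Optionally, if the design evaluation is ever re-run for another reason, use the complete model in SAP Table 2 (variances and residual error together), since Tables 3 and 4 do not show precision under that model. The documents do not establish that it would be worse.
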